5.0 STUDY TREATMENTS

5.1 RANDOMIZATION TO STUDY TREATMENT

Subjects will be screened by Investigators or qualified designees to assess eligibility for randomization into the study. An interactive voice response system (IVRS)/ interactive web response system (IWRS) will be used for assignment of treatment.

Subjects will be enrolled and randomized according to a fixed randomization scheme blocked by substudy (A-Study and B-Study will be randomized separately) and study investigative site. Severity of AD will be determined by MMSE at screening. ADAS-cog at Screening will be used as a stratification variable in the randomization scheme:

- ADAS-cog 19 or less.
- ADAS-cog more than 19.

Randomization will have balanced allocation (1:1) between azeliragon plus SoC and placebo plus SoC. Dropouts will not be replaced.

A randomization plan will be developed to guide the programming and security of the randomization scheme for this study.

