6.1 SCREENING

For logistical purposes, up to 60 days will be allowed for screening to confirm that participants meet all selection criteria for the study. It is strongly encouraged that the screening period is minimized to the shortest possible duration whenever possible. The investigator (or an appropriate delegate at the investigator site) will obtain informed consent from each subject, caregiver/informant, and where appropriate, legally authorized representative in accordance with Subject Information and Informed Consent/Assent (where this is in accordance with local laws, regulations and ethics committee policy). The screening assessments may be separated out into more than one visit if required. Refer to the Schedule of Events for a tabular presentation for screening activities.

The following activities will be completed:

- Complete informed consent/assent process (where this is in accordance with local laws, regulations and ethics committee policy) resulting in a signed ICF(s) by the appropriate parties.
- Assign screening identification number.
- Complete MMSE to determine subject eligibility. If subject is eligible based on the MMSE, proceed with the remainder of screening visit in any order.
- ADAS-Cog
- The Columbia Suicide Severity Scale (C-SSRS)
- CDR (calculation of both global score and sum of boxes score global)
- Demographic information (i.e., sex, date of birth, race/ethnicity).
- Complete medical and surgical history, including family medical history of dementia.
- Record and review concomitant medications and any discontinued medication in the 60 days prior to the Screening visit.
- History of drug, alcohol and tobacco use.

- Complete physical and neurological exams.
- Rosen-Modified Hachinski Ischemia Scale
- Height and body weight.
- Vital signs: blood pressure (supine), pulse rate.
- Single 12-lead electrocardiogram (ECG).
- Review of inclusion and exclusion criteria.
- Blood and urine specimens for safety laboratory tests (serum chemistry, hematology, UA) will be collected, in addition to the following:
 - Serum glucose and HbA1c;
 - Hepatitis screens (including hepatitis B surface antigen, hepatitis B core antibody, hepatitis B surface antibody, and hepatitis C antibody);
 - Syphilis test. If positive, a standard confirmation test will be obtained;
 - Thyroid function (T3, T4, and TSH);
 - Vitamin B12 (and MMA if indicated, e.g., if serum B12 level <211 pg/mL);

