7.2.1 Cognitive Assessments

Alzheimer's Disease Assessment Scale - Cognitive Subscale 70 point (ADAS-cog):

The ADAS-cog is a structured scale (approximately 40 minutes to complete) that evaluates memory, orientation, attention, reasoning, language and constructional praxis (Rosen, 1984). The ADAS-cog scoring range for the version used in this study is from 0 to 70, with higher scores indicating greater cognitive impairment. The ADAS-cog will be conducted at Screening, Baseline and at Months 3, 6, 9, 12, 15, 18, and 21 or in the event of early termination. The ADAS-cog should always be administered prior to other cognitive measures.

Mini Mental State Examination (MMSE): The MMSE is a brief 30-point test that is used to assess cognition (Folstein, 1975). It is commonly used to screen for dementia. In the time span of about 10 minutes, it samples various functions, including arithmetic, memory and orientation. The MMSE will be administered at Screening, Baseline, and at Months 3, 6, 12, 18, and 21 or in the event of early termination. Scores range from 0-30 with lower scores indicating greater cognitive impairment. Participants with scores of 21-26 will be eligible for participation in the study.

Controlled Oral Word Association Test (COWAT): The COWAT is a measure of verbal fluency in which the participant is asked to generate orally as many words as possible that begin with the letters “F”, “A”, and “S”, excluding proper names and different forms of the same word. (Borkowski, 1967, Loonstra 2001) For each letter, the participant is allowed one minute to generate the words. Performance is measured by the total number of correct words produced summed across the three letters. Perseverations (i.e., repetitions of a correct word) and intrusions (i.e., words not beginning with the designated letter) are noted.

Although fluency tests are sensitive to language dysfunction and deterioration of semantic knowledge, they can also reflect an inability to initiate systematic retrieval of information in semantic storage. The COWAT will be administered at Baseline, and at Months 3, 6, 12, 18, and 21 or in the event of early termination.

Category fluency test (CFT): Study participants are given one minute to provide exemplars of the category ‘animals’. The CFT will be administered at Baseline, and at Months 3, 6, 12, 18, and 21 or in the event of early termination.

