7.2.2 Functional/Global Assessments

Alzheimer's Disease Cooperative Study Activities of Daily Living Scale (ADCS-ADL): The ADCS-ADL is an activity of daily living inventory developed by the ADCS to assess functional performance in participants with AD (Galasko et al., 1997). Informants are queried via a structured interview format as to whether participants attempted each item in the inventory during the preceding 4 weeks, as well as their level of performance. The ADCS-ADL will be administered at Baseline, and at Months 3, 6, 12, 18, and 21 or in the event of early termination. Scores range from 0-78 with lower scores indicating greater functional impairment.

Clinical Dementia Rating Scale (CDR): The CDR scale is used as a global measure of dementia and is completed by a clinician in the setting of detailed knowledge of the individual patient collected from interviews with the patient and caregiver (Berg, 1988). The CDR describes 5 degrees of impairment in performance on each of 6 categories including memory, orientation, judgment and problem solving, community affairs, home and hobbies, and personal care. Much of the information

will therefore already have been gathered, either as part of normal clinical practice or as part of a research study. The interview takes approximately 40 minutes to administer.

CDR ratings are 0 for healthy individuals, 0.5 for questionable dementia and 1, 2 and 3 for mild, moderate and severe dementia as defined in the CDR scale. The scores for each category can also be summed and this is known as the sum of box score (CSR-SB). Sum of box scores range from 0 to 18 with higher scores indicating greater cognitive impairment.

The CDR will be conducted at Screening, Baseline and at Months 3, 6, 12, 18, and 21 or in the event of early termination. CDR should be done on a separate proximal visit day to avoid patient fatigue if feasible, particularly at baseline and Month 18.

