9.1 SAMPLE SIZE DETERMINATION

The primary objective is to evaluate the effect of azeliragon plus SoC on cognition and functional outcome by comparing azeliragon plus SoC with placebo plus SoC. The co-primary endpoints are change from Baseline on the ADAS-cog total score at Month 18 and change from Baseline on the CDR-sb total score at Month 18. The study includes AD patients with mild disease as defined by having a baseline MMSE of 21 through 26.

This trial includes two independent sub-studies, each of which is supported by randomization independently, because randomization by investigative site is used. Each sub-study is powered using $\alpha = 0.05$.

Approximately 160 subjects (80 per treatment group) will be enrolled and participate in the FDG-PET sub-study at select sites in the United States and Canada. The sample size for this sub-study was selected empirically.

Sample size calculations are done to power each study (A-study and B-study) separately. It is anticipated that each A-study and B-study will randomize approximately N=400 each.

Assuming a standard deviation of the change from Baseline to Month 18 in ADAS-cog of 9 (based on Study TTP488-203), using $\alpha = 0.05$, a total sample size of 282 patients in balanced allocation (141 patients per group) provides at least 90% power to detect a difference between treatment groups of 3.5 (based on data from mild AD patients in Study TTP488-203) using a 2-sided, 2-sample t-test. Assuming a dropout rate of 20% or less, randomization of 354 patients provides adequate statistical power for this study to demonstrate superiority of azeliragon plus SoC over placebo plus SoC based on the ADAS-cog.

Assuming a standard deviation of the change from Baseline to Month 18 in CDR-sb of 2.4, using $\alpha = 0.05$, a total sample size of 304 patients in balanced allocation (152 patients per group) provides at least 90% power to detect a difference between treatment groups of 0.9 (based on data from mild AD patients in Study TTP488-203) using a 2-sided, 2-sample t-test. Assuming a dropout rate of 20% or less, randomization of 380 patients provides adequate statistical power for this study to demonstrate superiority of azeliragon plus SoC over placebo plus SoC based on CDR-sb.

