### 5.2 Statistical Methodology for Efficacy Analysis

Efficacy evaluations will include the co-primary endpoints (ADAS-cog and CDR-sb), key secondary endpoint, secondary endpoints and other efficacy variables.

The primary analysis of efficacy endpoints will be done on the FAS with supportive and sensitivity analyses done to examine robustness against analysis assumptions and handling of missing data.

Statistical analysis will be done on the A-study and the B-study, independently, for the co-primary variables: change from baseline in ADAS-cog and change from baseline in CDR-sb. The A-study includes the first approximately 400 patients randomized, and the B-study includes the remaining approximately 400 patients randomized. For all other secondary variables and subgroup analyses, the study as a whole (A-study and B-study combined) will be used for inferential purposes. It is noted that randomization supports independent analysis of A-study and B-study.

The primary analysis will be done for the A-study and the B-study separately, and each will use  $\alpha = 0.049$ , which includes an adjustment of 0.001 for interim analyses performed by the Independent Data Monitoring Committee (IDMC), thereby preserving the overall study-wise  $\alpha = 0.05$ .

This study is randomized using site randomization; the study randomization also includes a randomization stratum for severity of AD using a cut-point of 19 on the ADAS-cog at the time of randomization (screening values are used, due to the expectation that a confirming evaluation would be done). Efficacy analyses will be done including randomization stratum as a main effect.

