### **5.2.1 Statistical Methodology for Primary Efficacy Analysis**

The primary analysis will be done on change from baseline in ADAS-cog and on change from baseline in CDR-sb.

The primary analysis will use the ITT methodology and a main-effects (for covariates) mixed-models for repeated measures (MMRM) methodology. The MMRM will utilize an unstructured covariance where the number of parameters is  $t(t+1)/2$  where  $t$  is the dimension of the covariance matrix, using PROC MIXED in SAS. In the unlikely event of lack of convergence, Toeplitz structure will be employed where the number of parameters is  $t$  where  $t$  is the dimension of the covariance matrix. Time is considered as a class variable. Analysis will include treatment, time, treatment-by-time interaction, Baseline as covariate, and baseline stratum as a covariate, and subject as a random effect (acknowledging that subject is a source of random variation). This method provides the primary treatment comparison at Month 18. Supportive modeling will also include MMRM main-effects model with treatment, time, and subject.

The primary analysis will also be done on randomization stratification subgroups defined by (1) baseline ADAS-cog 19 or less and (2) baseline ADAS-cog more than 19.

Multiple imputations (MI) will be used as an alternative for coping with missing data as supportive analyses with 100 invocations (acknowledging that more invocations are needed with more missing data). Monte Carlo methods are planned.

The MI analysis assuming Missing at Random (MAR) will be done as follows:

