- First, for patients with intermittent missing values, before performing the MI, a monotone missingness pattern will be created. Intermittent missing values will be imputed using the Markov Chain Monte Carlo (MCMC) methodology which assumes a multivariate normal distribution over all variables included in the imputation model. The imputation model will be performed by treatment group and will include age, sex, ApoE status, education level, body weight (or BMI), baseline stratum, baseline and observed values at Months 3, 6, 9, 12, 15 and 18. Months 9 and 12 are not included in the model for endpoints which were not scheduled to be assessed at those visits. The MI procedure in SAS will be used for this purpose and this first MI step is planned to be repeated 100 times, creating several different datasets with a monotone missing data structure. A unique seed value will be used in the MI procedure and documented to allow for replication. The imputation is based on the missing at random (MAR) assumption, i.e. the missing data are assumed to follow the same model as the other patients in their respective treatment arm.
- After this, the remaining missing data will be imputed using a method for monotone missingness, also based on the MAR assumption. Thus, for each of the 100 created datasets with a monotone missing data pattern, the MI procedure in SAS will be used to impute missing values based on a sequential procedure reflecting the monotone missing data pattern. A seed value of 446786 will be used for this second invocation of the MI procedure. Patients with the first missing value occurring at Month 3 will have their missing Month 3 value replaced by an imputed value from a regression model by treatment group with age, sex, ApoE status, education level, BMI, baseline stratum, and baseline as potentially predictive variables.
- In the next step, patients with the first missing value occurring at Month 6 will have their missing Month 6 value replaced by an imputed value from a regression model with Month 3 data, in addition to the variables listed above.
- The same procedure will be repeated for all other visits.

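### Both co-primary scales are scored twice before dosing, but the primary model uses only one score plus a two-level stratum: a small, free gain in precision is left unused

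*SAP*

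**What the plan says.** **Two pre-dose scores exist.** Protocol 7.2.1 states: "The ADAS-cog will be conducted at Screening, Baseline and at Months 3, 6, 9, 12, 15, 18, and 21". Protocol 7.2.2 states: "The CDR will be conducted at Screening, Baseline and at Months 3, 6, 12, 18, and 21". The screening list in protocol 6.1 asks for the sum of boxes as well as the global score: "CDR (calculation of both global score and sum of boxes score global". The activity schedules in the protocol (Table 1) and the SAP (Section 12) both show the two scales at Screening and Baseline.

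**Both should be complete at Screening.** Protocol 5.1 makes the first ADAS-cog part of randomisation: "ADAS-cog at Screening will be used as a stratification variable in the randomization scheme", with the cut at 19. Inclusion criterion 9 needs a CDR global score at Screening.

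**The primary model.** SAP 5.2.1 specifies: "Analysis will include treatment, time, treatment-by-time interaction, Baseline as covariate, and baseline stratum as a covariate". Protocol 9.5.2 gives the same covariates. Neither uses a continuous screening score. The supportive ANCOVA and multiple-imputation (MI) models in SAP 5.2.1 do not use one either, although the MI predictor list is longer than the primary covariate list and includes "ApoE status, education level, body weight (or BMI), baseline stratum". No reason for the omission is given.

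**The concern.** A single ADAS-cog or CDR-sb score is the patient's underlying level plus measurement error. With any error at all, a second score taken within 60 days before dosing says something about that level that the Baseline score does not, and so helps to predict Month 18. For ADAS-cog the stratum recovers part of this information. For CDR-sb the stratum comes from a different scale and recovers little.

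What is at stake is precision. The residual variance of the Month 18 contrast is slightly larger than it need be. SAP 5.2.1 (adjustments for multiplicity) requires both endpoints to succeed in both sub-studies, and SAP Section 2 makes the MRI and secondary tests conditional on that. A small loss per test therefore counts four times.

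**Working it through.** **Step 1. Reproduce the plan.** Inputs from protocol 9.1: SD of change 9 and 2.4, differences 3.5 and 0.9, 90% power, two-sided t-test, 20% dropout. Normal approximation: n per group = 2(1.960 + 1.282)² × SD²/difference².

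- ADAS-cog: 2 × 10.507 × 81/12.25 = 138.96, so 139. The exact t calculation gives 140 at alpha 0.05 and 141 at 0.049, against 141 stated. 282/0.8 = 352.5, or 354 with equal arms, as stated.
- CDR-sb: 2 × 10.507 × 5.76/0.81 = 149.4, so 150. Exact t gives 151 at alpha 0.05 and 152 at 0.049, against 152 stated. 304/0.8 = 380, as stated.

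The tests are run at 0.049 (SAP 5.2), "which includes an adjustment of 0.001 for interim analyses performed by the Independent Data Monitoring Committee (IDMC". With about 400 randomised per sub-study and 20% dropout, 160 per arm remain. Unadjusted power at 0.049 is then 93.3% for ADAS-cog and 91.5% for CDR-sb.

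**Step 2. Model for the gain.** Screening = T + e0, Baseline = T + e1, Month 18 = (1 + g)T + D + e2, where T is the true pre-dose level, D is progression and the e's are errors. Let R be test-retest reliability, S the baseline SD and V = R × S² the variance of T. The SD of change is held at the planned 9 or 2.4, so:

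Var(D + e2) = SD² − g²V − (1 − R)S².

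Residual variance of Month 18, ignoring the stratum:

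- given Baseline: (1 + g)²V(1 − R) + Var(D + e2)
- given Baseline and Screening: (1 + g)²V(1 − R)/(1 + R) + Var(D + e2)

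The stratum was then added to both models by simulation (1,000,000 patients per scenario).

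**Assumptions not in the documents:** R from 0.70 to 0.95; S from 5 to 8 (ADAS-cog) and 1.2 to 2.0 (CDR-sb); g = 0 or 0.3; stratum cut at the median; correlation 0.5 between screening CDR-sb and the score behind the stratum.

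**Step 3. Worked cases (R = 0.8, g = 0).**

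- ADAS-cog, S = 6: V = 28.8 and Var(D + e2) = 81 − 7.2 = 73.8. Given Baseline: 5.76 + 73.8 = 79.56. Given both: 3.2 + 73.8 = 77.0. The cut is 2.56/79.56 = 3.2%. With the stratum already in the model it falls to 2.0% (residual SD 8.86 to 8.77).
- CDR-sb, S = 1.5: V = 1.8 and Var(D + e2) = 5.76 − 0.45 = 5.31. Given Baseline: 5.67. Given both: 5.51. The cut is 0.16/5.67 = 2.8%, or 2.6% with the stratum (residual SD 2.38 to 2.35).

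**Step 4. Range, with the stratum in both models (160 per arm, alpha 0.049).**

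| Scale | Case | Variance cut | Power |
|---|---|---|---|
| ADAS-cog | lowest (S 5, R 0.95, g 0) | 0.6% | 93.4% to 93.5% |
| ADAS-cog | worked case | 2.0% | 94.0% to 94.4% |
| ADAS-cog | highest (S 8, R 0.70, g 0.3) | 6.6% | 94.5% to 95.8% |
| CDR-sb | lowest (S 1.2, R 0.95, g 0) | 0.6% | 91.5% to 91.7% |
| CDR-sb | worked case | 2.6% | 92.0% to 92.6% |
| CDR-sb | highest (S 2.0, R 0.70, g 0.3) | 9.4% | 91.9% to 94.2% |

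In patients: multiplying the Step 1 results by 0.97 or 0.95 takes the ADAS-cog n per group from 139 to 135 or 133, and the CDR-sb n from 150 to 145 or 142.

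**Step 5. All four tests.** Treating the tests as independent, the worked cases give (0.9397 × 0.9197)² = 74.7% without the screening scores and (0.9440 × 0.9262)² = 76.4% with them. Positive correlation between the two endpoints would raise both figures.

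**The case against.** The strongest reply is that nothing is broken. Adjusting for Baseline and the randomisation stratum is sound, the sample size takes no credit for any covariate, and each test already has more than 90% power at the planned size. All of this stands, and it fixes the point at low severity.

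The second reply is that the gain could be less than shown. The figures let the coefficients be the best ones for Month 18, whereas SAP 5.2.1 keeps covariates as main effects only. One common slope across visits may recover less. This also stands, and the fix allows for it.

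The third is that the change is more than an editorial one. SAP Section 5 says that the protocol fully specifies the primary analysis, SAP 6.2 treats the primary methods as fixed, and SAP 1.9 declares a single departure from the protocol. That raises the formality needed but does not bar the change. The SAP introduction provides for tracked amendments after finalisation, and protocol 9.0 lets the SAP supersede the protocol.

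Some stronger readings are tempting but unsupported:

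- **A much larger gain.** Correlations chosen freely can give a large cut. With 0.80 both between the two pre-dose scores and between each of them and Month 18, the CDR-sb cut is 1 − (1 − 2 × 0.64/1.8)/(1 − 0.64) = 19.8%. With equal reliability, however, this makes true scores 18 months apart correlate perfectly. If Month 18 moves one for one with Baseline, it needs baseline SDs of 9 × 0.8/0.6 = 12 and 2.4 × 0.8/0.6 = 3.2, which are hard to credit with entry limited to MMSE 21 to 26 and CDR global 0.5 or 1. It also leaves the stratum out of the comparison.
- **Age and ApoE belong in the primary model because the MI model uses them.** An imputation model richer than the analysis model is ordinary practice, and the documents give no figure for what these variables would add.
- **Missing at random becomes more credible.** Nothing in the documents lets this be sized, and SAP 5.2.1 already plans MI with extra predictors, a tipping-point analysis and a placebo-based analysis.

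**Conclusion.** The point holds as a free improvement of low severity. A pre-randomisation measurement of each co-primary scale is collected and then reduced to two levels (ADAS-cog) or left out (CDR-sb). The direction of the gain follows from measurement error alone. Its size rests on the assumed reliability and baseline SD, neither of which the documents give: a few percent of residual variance in typical cases, usually more for CDR-sb than for ADAS-cog, and from a fraction of a point to about two points of power per test. In the worked cases the chance of passing all four tests rises by a little under two points, if they are treated as independent.

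A reader might infer that the trial is underpowered or that the primary estimate is biased. Neither follows: the stated sample sizes reproduce and the planned adjustment is valid.

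**What to change.** By formal amendment, before the first sub-study is unblinded (protocol 11.1 has the two locked and unblinded separately):

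1. In SAP 5.2.1, add the continuous Screening score of the same scale as a covariate in both co-primary MMRMs. Keep the Baseline score and the randomisation stratum.
2. If the full Month 18 gain is wanted, add a covariate-by-time term and revise the SAP 5.2.1 sentence that rules out interactions with covariates.
3. Carry the same covariate into the matching ANCOVA and MI models.
4. List the change in SAP 1.9 as a modification from protocol 9.5.2.
5. Define the efficacy Baseline as the Baseline-visit score. SAP 6.1 defines Baseline for safety evaluations only, and the two pre-dose scores must not be interchangeable once both are in the model.

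The cost is the amendment itself and one degree of freedom per model, or one per visit with the time term (six post-baseline ADAS-cog visits, four CDR visits), against about 320 evaluable patients per sub-study. No new data are needed, and the unadjusted power statements remain valid.
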